5.3 Treatment Assignment Procedures

5.3.1 Randomization Procedures

Participants will be randomized via permuted block randomization. Randomization will be recorded on an electronic log by the pharmacy. Study investigators and subjects will be blinded.

5.3.2 Masking Procedures

Participants will be provided masked study medicine, shipped by courier (e.g. FedEx). The intervention vs. placebo will not be identical; however, participants and outcome assessors will be masked to their assignment.

5.3.3 Reasons for Withdrawal

Participants may withdraw at any time point at their discretion.

5.3.4 Handling of Withdrawals

Withdraws will be counted as failures for the secondary endpoint of completion of study medication.

5.3.5 Termination of Study

This study may be prematurely terminated if there is sufficient reasonable cause, including but not limited to:

- Unexpected, significant, or unacceptable risk to subjects
- Interim analyses by the DSMB.
- Insufficient compliance with protocol requirements
- Data are not sufficiently complete and/or not evaluable

• Regulatory authorities decide that study should be terminated

If the study is prematurely terminated for harm, current subjects will complete follow up, and no further subjects will be enrolled. If the study is terminated due to benefit, then the study will immediately convert into an open-label prospective cohort to collect further observational data on the safety and efficacy of the intervention, up to the IRB approved recruitment limit.

6 STUDY INTERVENTION/INVESTIGATIONAL PRODUCT

6.1 Study Product Description

6.1.1 Acquisition

[figure not shown]
FDA-approved formulation of hydroxychloroquine will be purchased.

6.1.2 Formulation, Packaging, and Labeling

The study medicines will be packaged by the Investigational Drug Services. Dispensed medications will be delivered by courier (e.g. FedEx) to study participants.

6.1.3 Drug Description:

Hydroxychloroquine sulfate

6.1.4 Formulation:

[figure not shown]
200mg tablet (= 155 mg base of chloroquine)

6.1.5 Pharmacokinetics:

- Absorption: Rapid and almost completely
- Distribution: Widely distributed into body tissues
- Metabolism: Partially hepatic to main metabolyte of desethylchloroquine
- Excretion: Urine (>=50% as unchanged drug); acidification of urine increases elimination
- $C_{max} = 1.2 \text{ nmol/mL} = 1.2 \mu \text{mol/L} = 1.2 \mu M$ at 400mg single dose.[5,7]
- $T_{max} = 2.4$ hours
- T_{1/2} = 172 + 39 hours = 7.1 +1.6 days
- AUC_{last} = 75.4 + 47 nmol/h/mL
- This C_{max} is in the therapeutic window for SARS-COV2 activity.
- Steady-state trough concentrations for 400mg twice-weekly dosing is expected to be above 0.72 μ M, which is above the EC50 of viral inhibition.

PREP COVID-19

Version 1.0 27 March 2020

6.1.6 Product Storage and Stability

Store at room up to 30° C (86° F). Dispense in a tight, light-resistant container.

6.2 Dosage, Preparation, and Administration of Investigational Product

6.2.1 Drug/Device Handling: Hydroxychloroquine or placebo will be dispensed by the investigational Pharmacy. To do so, study investigators will send a prescription to the Pharmacy, the pharmacy will randomize the subject, and dispense the appropriate study medicine. The medicine will then be provided to research volunteers via courier delivery in the United States.

6.3 Modification of Investigational Product for a Participant

With mild side effects, participants may be instructed to split the 2 tablet weekly dosing into multiple times on the same day (for example, one tablet in the morning, followed by one tablet at night).

In the event of substantial side effects, participants may discontinue the study medication.

In the event of the development of acute kidney injury with creatinine clearance <30 mL/min, the dose should be reduced by half.

6.4 Accountability Procedures for the Investigational Product:

Accountability will be via self-report at weekly virtual visits.

[figure not shown]
6.5 Assessment of Subject Compliance

Adherence will be via self-report at weekly virtual visits.

6.6 Concomitant Medications/Treatments

Participants may receive other concomitant medications or therapies and will be asked to report these.

Study Schedule

PREP COVID-19

Version 1.0 27 March 2020

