4.3.2 Randomization

- Participants will be randomized at the investigation pharmacy
- The investigational pharmacy will dispense masked study medicine (hydroxychloroquine or placebo)
- The study medicine will be shipped to participants to arrive ~1 day after enrollment
- 4.3.3 Day 1 Virtual visit
 - Verify receipt of study medicine
 - Clinical status check-in
 - Begins taking study medicine (2 tabs), then 2 tabs in 6-8 hours
 - Query for symptom status
 - Query for hospitalization or SAEs
- **4.3.4** Weekly Virtual visit
 - Clinical status check-in for COVID-19 symptoms
 - Assessment of adherence and side effects by self-report
 - Continue study medicine up to 12 weeks
 - Query for study medicine side effects since enrollment
 - Query for SARS-CoV-2 testing
 - Query for hospitalization or SAEs
- **4.3.5** Study termination virtual visit (to be completed on or shortly after the common closing date for the study)
 - Clinical status check-in for COVID-19 symptoms
 - Query for study medicine adherence and side effects since enrollment
 - Query for SARS-CoV-2 testing
 - Query for hospitalization or SAEs
 - Query for pregnancy status
 - Final outcome assessment
- **4.4** Individually identifiable health information: Name, date of birth, and phone number will be collected so as to prescribe study medication. Email addresses will be collected for communication. If participants are hospitalized, the hospitalization date will be collected.

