5.2 Subject Exclusion Criteria

- Active COVID-19 disease
- Confirmed prior COVID-19 disease
- Current fever, cough, shortness of breath
- Contraindication or allergy to chloroquine or hydroxychloroquine
- Prior retinal eye disease
- Known Chronic Kidney disease, Stage 4 or 5 or dialysis.
- Known glucose-6 phosphate dehydrogenase (G-6-PD) deficiency.
- Weight <40 kg
- Current use of hydroxychloroquine or cardiac medicines of flecainide, amiodarone, digoxin, procainamide, or propafenone
 - Current use of medications with known significant drug-drug interactions:

artemether, lumefantrine, mefloquine, tamoxifen or methotrexate.

Rationale for inclusion / exclusion criteria:

Healthcare workers at high risk for COVID-19 exposures include:

- Persons primarily working in emergency departments (physicians, nurses, ancillary staff, triage personnel)
- Persons primarily working in intensive care units (physicians, nurses, ancillary staff, respiratory therapists)
- Persons performing aerosol generating procedures: ex. Anesthesiologists, nurse anesthetists (CRNAs)
- First responders: ex. EMTs, paramedics

In clinical practice of tropical medicine, chloroquine or hydroxychloroquine are prescribed without any baseline laboratory testing or monitoring.

Age criteria are meant to increase the propensity to follow up and minimize dropouts.

Chronic use of hydroxychloroquine for >1 year can cause retinopathy or cardiomyopathy, thus persons with baseline conditions will be excluded. Study medicine is excreted via the kidney with dose reduction recommended in CrCl <30 cc/min (Stage 4 Kidney Disease). G-6-PD deficiency is listed as a caution on the FDA label. G-6-PD testing is not routinely performed in clinical care prior to giving hydroxychloroquine prescriptions (unlike with primaquine). Medication exclusions are for possible drug-drug interactions, particularly with cardiac arrhythmia medicines with a caution on the FDA-package insert.

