6.8 Enrollment/Baseline

- **6.8.1** Randomization (Day 0)
 - Participants will be randomized by a computer-generated algorithm using a permuted block randomization sequence
 - Investigational pharmacy will dispense the masked study medicine (12 week supply)
 - Study personnel will then courier study medicine to the participant
 - Participant will be sent an email to expect the medication to arrive the following day

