7.2 Laboratory Evaluations

There are no laboratory evaluations in the protocol. There is an opportunity for participants to participate in an optional lab-based sub-study. Details in Appendix A.

Clinical outcomes are by self-report.

SARS-COV2 positivity is by self-report.

Informed consent will request permission to contact local public health authorities or their medical provider in the event of loss to follow up or COVID-19 disease. Public health authorities or medical providers may verify confirmatory laboratory results.

There is no incentive to be dishonest, and we believe healthcare workers in particular will take their responsibilities seriously.

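### Section 5.2 excludes users of ten drugs for possible interactions, but 6.6 permits other medicines on study without excepting those drugs and attaches no action to a report

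*Combined protocol and SAP*

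**What the plan says.** Section 5.2 has two medication exclusions. The first is "Current use of hydroxychloroquine or cardiac medicines of flecainide, amiodarone, digoxin, procainamide, or propafenone". The second covers drugs described there as having significant known interactions: "artemether, lumefantrine, mefloquine, tamoxifen or methotrexate". The rationale that follows the list reads: "Medication exclusions are for possible drug-drug interactions, particularly with cardiac arrhythmia medicines with a caution on the FDA-package insert".

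For the period after enrolment, 6.6 says: "Participants may receive other concomitant medications or therapies and will be asked to report these". It names no prohibited drug and no exception.

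Section 6.3 governs changes to study drug. Doses may be split for mild side effects and halved for acute kidney injury with creatinine clearance below 30 mL/min. For more serious intolerance it says: "In the event of substantial side effects, participants may discontinue the study medication". Section 5.3.3 leaves withdrawal to the participant.

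On the setting, the pharmacy dispenses 12 weeks of masked medicine at the outset (6.8.1) and clinical status is self-reported (7.1). On laboratory work, 7.2 says: "There are no laboratory evaluations in the protocol". Section 6.12 provides an email address that reaches an on-call study physician, and a sick-visit form that can be completed repeatedly.

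**The concern.** An entry exclusion made for a drug interaction protects participants only while the two drugs stay apart. The reason for it does not lapse at randomization; it applies for as long as hydroxychloroquine is taken. Read literally, 6.6 permits on study the combinations that 5.2 screens out.

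The design makes a written rule more useful than it would be in a clinic-based trial. Participants hold their whole supply, nobody sees them in person, and assignment is masked. A participant who is prescribed amiodarone in week 5, for example, cannot be assumed to know whether study drug is hydroxychloroquine. The protocol does not tell that participant, or the study physician who receives the report, to stop study drug. What is at stake is avoidable exposure to a combination that the protocol itself wished to avoid. The efficacy comparison is not at stake.

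**Working it through.** The plan gives no figure on this point to reproduce. The check is a count, a side-by-side reading and some simple arithmetic on exposure.

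**1. Drugs concerned.** Cardiac: flecainide, amiodarone, digoxin, procainamide, propafenone = 5. Others: artemether, lumefantrine, mefloquine, tamoxifen, methotrexate = 5. Total 5 + 5 = 10. Hydroxychloroquine is also excluded at entry, but it is the study drug and the interaction rationale does not explain its exclusion, so it is not counted here.

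**2. On-study text that could supply an action.**

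| Section | What it covers | Action on study drug if a listed drug is started |
|---|---|---|
| 2.3.1 | Spacing of antacids (not on the 5.2 list) | None |
| 4.3, 6.9, 6.10 visit lists | Symptoms, adherence, side effects, testing, SAEs | None |
| 5.3.3 | Withdrawal at the participant's discretion | None required |
| 6.3 | Side effects; acute kidney injury | None |
| 6.6 | Other medicines allowed; reports requested | None |
| 6.11 | COVID-19 symptoms referred to own provider | None |
| 6.12 | Physician contact and sick-visit form | None specified |

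**3. The plan's own comparator.** Section 5.2 excludes Stage 4 or 5 kidney disease and cites dose reduction below a clearance of 30. Section 6.3 carries that concern into the study: if clearance falls below 30 mL/min, the dose is halved. The renal exclusion therefore has an on-study counterpart. The ten-drug exclusion does not.

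**4. Exposure window.** If a listed drug is started at the end of week w of 12, the maintenance doses of 400 mg still to come are at most (12 − w) × 1 in the weekly arm and (12 − w) × 2 in the twice-weekly arm.
- w = 4: 8 × 1 = 8 doses, or 8 × 2 = 16 doses.
- w = 8: 4 × 1 = 4 doses, or 4 × 2 = 8 doses.

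These are upper limits, since the trial may close before a participant reaches 12 weeks. They describe how long the missing rule would apply, not interaction risk.

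**5. Share on active drug.** With 1165 per group (10.2), 2 × 1165 / (3 × 1165) = 2330 / 3495 = 67%. The remaining 33% receive placebo, so about a third of any doses stopped under an all-arm rule would be placebo if starts and stopped doses are spread evenly across arms.

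**6. How fast a stop acts.** Section 6.1.5 gives a half-life of 172 hours, and 172 / 24 = about 7.2 days. Assuming simple exponential decline, the fraction left one week (168 hours) after the last dose is 0.5^(168/172) = 0.51. About half the drug is still present, so a report made before the new drug is started is worth more than one made afterwards.

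**The case against.** The strongest reply is that the plan is not silent. Section 6.6 asks for reports, 6.12 puts the participant in touch with a study physician at any time, and a participant may stop whenever they choose. Participants are emergency, intensive-care, anesthesia and first-responder staff who screened themselves against a list naming these drugs. The trial is openly pragmatic and leaves management of hospitalized participants to local providers (8.4). All of this stands, and it narrows the point: what is missing is the trigger for using the route and the action that follows. A general invitation to raise concerns does not say that starting a listed drug is a reason to make contact.

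A second reply is that the warning may sit in consent material, the study schedule or the weekly eCRF, none of which is available here. That also stands. A reader might infer that participants are never told which medicines to avoid; the documents do not support that. Even with such a warning, 6.6 would still permit the combinations without exception.

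A reader might also infer that harm from a combination would go unnoticed. That is too strong. The Day 1, weekly and termination visits in 4.3 each include "Query for hospitalization or SAEs", side effects are asked about during follow-up, and the SAE definition in 8.3.1 reaches important medical events without hospitalization. These checks do, however, work after the event.

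Finally, a reader might want a number of people affected or harmed. The documents give no rate at which participants start these drugs and no interaction risk, so any headcount would simply restate an assumed rate. None is offered.

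**Conclusion.** The gap is real but limited. As written, 6.6 permits during the study what 5.2 excludes at entry, and no section available for review ties an action on study drug to starting one of the ten drugs. The renal rule shows that the plan already turns one entry exclusion into an on-study action, so the omission does not follow a consistent policy of leaving such matters out.

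The size is modest. The frequency is unknown and probably low, no harm rate is claimed, and no sample size, power, alpha or primary analysis is affected. The case for acting rests on the low cost of the rule and on the setting of masked, remote, self-reported dosing. It assumes that the consent text and forms not available here do not already contain an equivalent instruction. If they do, 6.6 should still be brought into line with them.

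**What to change.** Add to 6.6:

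1. The medicines excluded in 5.2, including non-study hydroxychloroquine, are not to be combined with study drug. For hydroxychloroquine the reason is double dosing.
2. A participant who is to start one reports it through the email or form already described in 6.12, before the first dose where possible. Urgent treatment is not delayed for this.
3. Study drug is stopped in any arm, without unblinding, while the listed drug is in use. It resumes only if the listed drug has ended and the on-call study physician agrees.
4. Weekly follow-up continues and the participant stays in the intention-to-treat analysis (10.4).

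The cost is a few sentences of protocol text, a few missed doses (about a third of them placebo) and a few extra physician calls. Given the half-life of about 7 days, a stop made after the new drug has been started acts slowly, so the rule reduces overlap but cannot abolish it.

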6.7 Screening

- Baseline screening for eligibility
- Informed consent by self-administered
- This will be performed via a web-based form. Eligibility criteria will be by self-report.

6.8 Enrollment/Baseline

- **6.8.1** Randomization (Day 0)
 - Participants will be randomized by a computer-generated algorithm using a permuted block randomization sequence
 - Investigational pharmacy will dispense the masked study medicine (12 week supply)
 - Study personnel will then courier study medicine to the participant
 - Participant will be sent an email to expect the medication to arrive the following day

6.9 Follow-up

- Day 1 Visit
 - Participant will confirm receipt of study medication

Weekly visits

- Participant clinical status check-in
- Assess adherence to study medication and side effects

6.10 Final Study Visit

- Participant clinical status check-in
- Assess adherence to study medicine

6.11 Early Termination Visit

If participants develop symptoms of coronavirus, they will be directed to their healthcare provider and/or local public health authority. We request to follow up hospitalized healthcare workers with suspected COVID-19 up to 90 days beyond the closing date to assess final outcomes.

6.12 Unscheduled Visit

Subjects will be provided a central email contact: [contact] as a contact point for questions or concerns. This email will forward to an on-call study physician who will call the participant to resolve their concerns.

Additionally, email communications will contain a URL for a sick visit web-form that participants can note their current development of symptoms of medication side effects. This will be the same follow-up eCRF sent on weekly visits. This can be completed multiple times.

7 STUDY PROCEDURES/EVALUATIONS

7.1 Clinical Evaluations

Clinical evaluations will be by self-report.

7.2 Laboratory Evaluations

There are no laboratory evaluations in the protocol. There is an opportunity for participants to participate in an optional lab-based sub-study. Details in Appendix A.

Clinical outcomes are by self-report.

SARS-COV2 positivity is by self-report.

Informed consent will request permission to contact local public health authorities or their medical provider in the event of loss to follow up or COVID-19 disease. Public health authorities or medical providers may verify confirmatory laboratory results.

There is no incentive to be dishonest, and we believe healthcare workers in particular will take their responsibilities seriously.

8 ASSESSMENT OF SAFETY

8.1 Specification of Safety Parameters

Hydroxychloroquine has a track record of safety since its FDA-approval in 1955. As an already, FDA-approved medicine, this trial is designed as a pragmatic trial in the setting of a public health emergency.

8.2 Methods and Timing for Assessing, Recording, and Analyzing Safety Parameters

8.2.1 Adverse Events

Hydroxychloroquine has an excellent safety track record, being first FDA-approved in 1955. Adverse events will not be captured unless they result in hospitalization. See Serious Adverse Events below.

Expected adverse events would include normal events within the general population as well as COVID19-related disease events which may include the need for hospitalization, pneumonia, respiratory failure, sepsis, and death.

8.2.2 Reactogenicity (for Vaccine Studies and Some Therapeutic Trials)

Not applicable

8.2.3 Serious Adverse Events

Hospitalization or death are protocol-defined endpoints.

8.2.4 Procedures to be Followed in the Event of Abnormal Laboratory Test Values or Abnormal Clinical Findings

Not applicable

8.3 **Reporting Procedures**

8.3.1 Serious Adverse Events

An AE or suspected adverse reaction is considered a serious adverse event (SAE) if it results in any of the following outcomes:

PREP COVID-19

- Death,
- a life-threatening adverse event (as below),
- hospitalization,
- a persistent or significant incapacity or substantial disruption of the ability to conduct normal life functions, or
- congenital anomaly/birth defect.
- Important medical events that may not result in death, be life-threatening or require hospitalizations may be considered serious when based upon appropriate medical judgment they may jeopardize the participant or subject and may require medical or surgical intervention to prevent one of the outcomes listed in this definition.
- Examples of such medical events include allergic bronchospasm requiring intensive treatment in an emergency room or at home, blood dyscrasias or convulsions that do not result in inpatient hospitalization, or the development of drug dependency or drug abuse.
- Life-threatening adverse event. An AE is considered "life-threatening" if, in the view of either the site principal investigator or sponsor, its occurrence places the subject at immediate risk of death. It does not include an AE that, had it occurred in a more severe form, might have caused death. For life-threatening AEs, subjects would be recommended /expected to be hospitalized.

Based on the known safety track record of hydroxychloroquine, this pragmatic protocol will focus on death, life-threatening AEs, and hospitalizations. Incapacity / permanent disability is a possibility with COVID19, but this is not associated with hydroxychloroquine. In the event of incapacity, the subject would be expected to be hospitalized.

Hydroxychloroquine and chloroquine are not known to cause teratogenic events and are viewed as safe in pregnancy, especially with short term use. With this trial's sample size, this will not further delineate this risk. COVID-19 disease may indeed be teratogenic. For women who are pregnant, we will ask to follow them through the end of their pregnancy.

Thus the hospitalization or death secondary endpoint will capture relevant SAEs.

